In Part A, all SOT recipients who were unvaccinated prior to enrollment will receive 2 doses of 100 μ g of mRNA-1273 28 days apart (window of -3/+7 days for the second dose) (Group A1). The SOT recipients will be offered the opportunity to receive a third primary dose of mRNA-1273 at Day 85 (window of -3/+7 days for the third dose) as per the EUA Fact Sheet available at the time of protocol finalization (Group A2). All healthy participants will receive 2 doses of 100 μ g of mRNA-1273 28 days apart (window of -3/+7 days for the second dose) (Group A5). The SOT recipients who were previously vaccinated with 2 doses of Moderna COVID-19 vaccine under the EUA prior to enrollment will receive dose 3 on Day 1 (Group A3). These participants will be referred to as “previously vaccinated” throughout this document. Under Amendment #4, unvaccinated SOT participants who will be enrolled will be given 3 100 μ g doses in Part A then proceed to Part B to receive a 100 μ g booster dose. Under Amendment #4, SOT participants previously vaccinated with 2 doses of Moderna COVID-19 vaccine outside of the study who will be enrolled will receive a third 100 μ g dose in Part A then proceed to Part B to receive a 100 μ g BD.

In Part B, all participants in Part A will be offered a 100 µg BD of mRNA-1273 at least 4 months from the last dose. SOT recipients who completed primary COVID-19 vaccination series under EUA will receive a 100 µg BD on BD-D1 (Group B4).

Study Arm	Part A	Doses in P304 Part A	Part A Dose	Move on to Part B?	Part B	Doses in P304 Part B	Part B B-Dose	Total Doses in P304
SOT Recipient Cohorts								
Unvaccinated participants who consent to receive only 2 doses in Part A (Days 1 and 29)	Group A1	2	100 µg		NA	N/A	N/A	2
Unvaccinated participants who consent to receive 3 doses in Part A (Days 1, 29, and 85)	Group A2	3	100 µg	➡	Group B2	1	100 µg	4
Participants previously vaccinated with 2 doses of the Moderna COVID-19 vaccine under the EUA who consent to receive a third dose in Part A (Day 1)	Group A3	1	100 µg	➡	Group B3	1	100 µg	2
SOT recipients who completed primary vaccination with an mRNA or non-mRNA COVID-19 vaccine outside mRNA-1273-P304 who consent to receive 1 booster dose (in Part B)	N/A	N/A	N/A		Group B4	1	100 µg	1

Healthy Adult Cohort								
Healthy adults who consent to receive 2 doses in Part A (Days 1 and 29)	Group A5	2	100 µg		Group B5	1	100 µg	3

Abbreviations: B-Dose = booster dose; EUA = Emergency Use Authorization; SOT = solid organ transplant

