7.1.6. Assessments for SARS-CoV-2 Infection

Study participants will have NP samples collected for SARS-CoV-2 testing by RT-PCR at time points specified in the applicable SoE ([Section 10.1](#)). A study illness visit or a consultation will be arranged within 72 hours or as soon as possible to collect an NP or nasal swab sample (NP is preferred) to ascertain the presence of SARS-CoV-2 via RT-PCR if a participant experiences any of the following:

- Signs or symptoms of SARS-CoV-2 infection as defined by the CDC ([CDC 2020a](#))
- Close contact exposure to an individual confirmed to be infected with SARS-CoV-2
- MAAE suggesting a SARS-CoV-2 infection

If the participant had known close contact exposure to COVID-19 (eg, close contact exposure to someone with confirmed COVID-19), it will be captured in the COVID-19 exposure form.

If scheduled, the study illness visit may collect additional clinical information at the investigator's discretion, including but not limited to medical history, physical examination, blood sampling for

clinical laboratory testing, and nasal, saliva, and/or NP swab sampling for viral PCR (including multiplex PCR for respiratory viruses, including SARS-CoV-2) to evaluate the severity of the clinical case. Radiologic imaging studies may be conducted. During this visit, a blood sample will also be collected for immunologic assessment of SARS-CoV-2. All findings will be recorded in the eCRF.

If participants are confirmed to have SARS-CoV-2 infection, the investigator will notify the participant and the participant's primary care physician of the diagnosis. If the study participant does not have a primary care physician, the investigator will assist them in obtaining one. The participant will also be instructed on infection prevention measures consistent with local public health guidance.

Any confirmed symptomatic SARS-CoV-2 infection occurring in participants will be captured as an MAAE along with relevant concomitant medications and details about severity, seriousness, and outcome. Additionally, a convalescent visit will be scheduled approximately 28 days (+7 days) after diagnosis ([Section 7.3.2](#)). At this visit, an NP swab sampling for viral PCR and a blood sample will be collected for potential immunologic assessment of SARS-CoV-2 infection

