8. Vital signs are to be measured pre- and post-dose on days of injection (Day 1, Day 29, and Day 85). When applicable, vital signs should be measured before blood collection. Participants who are febrile (body temperature $\geq 38.0^{\circ}\text{C}/\geq 100.4^{\circ}\text{F}$) before injection on Day 1, Day 29, or Day 85 must have the visit rescheduled within the relevant visit window to receive the injection. Afebrile participants with minor illnesses can be enrolled at the discretion of the investigator.
9. The pregnancy test at Screening, Day 1, and before the second and third study injections will be a point-of-care urine test. At the discretion of the investigator, a pregnancy test either via blood or point-of-care urine test can be performed at any time.
10. Samples for safety laboratory assessments (serum creatinine, urine protein, and UPCR for kidney transplant recipients only; ALT, AST, ALP, and bilirubin for liver transplant recipients only) must be collected prior to dosing on Day 1, Day 29, and Day 85.
11. After Day 113, the investigator will review standard-of-care kidney and liver laboratory assessments and report any laboratory-related AEs and suspected or confirmed events of organ transplant rejection until the EOS.
12. Samples for immunogenicity (bAb against SARS-CoV-2 spike protein and neutralizing antibody against SARS-CoV-2) and assessment of SARS-CoV-2 bAb against the nonvaccine antigen (nucleocapsid protein) must be collected prior to dosing on Day 1, Day 29, and Day 85.
13. For assessment of cellular immune response, blood samples will be collected on Day 1 (prior to dosing), Day 36, and Day 92 from a subset of at least 50 unvaccinated SOT recipients (kidney or liver).
14. The NP swab sample will be collected prior to dosing and used to ascertain the presence of SARS-CoV-2 via RT-PCR.

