**For calculation regarding antibody levels/concentrations**, antibody values reported as below LLOQ will be replaced by  $0.5 \times \text{LLOQ}$ . Values that are greater than the upper limit of quantification (ULOQ) will be used as available. Values that are reported as greater than ULOQ ( $>\text{ULOQ}$ ) without actual values will be replaced by ULOQ for analysis. Missing results will not be imputed, unless otherwise specified.

**The following Analysis Stages** will be defined for use in this study:

- Up to 28 days after any vaccination:

This stage starts at the day of each vaccination and continues through the earliest date of (the day of each vaccination and 27 subsequent days, next vaccination [if applicable]). This analysis period will be used as the primary analysis period for safety analyses (including unsolicited AEs), except for solicited ARs, unless specified otherwise.

- Throughout the study period:

For subjects in Part A, this analysis period starts at the first study injection on Day 1 and continues through the earliest date of study completion (or prior to BD), discontinuation from the study, or death.

For subjects in Part B, this analysis period starts at the BD on BD-Day 1 and continues through the earliest date of study completion, discontinuation from the study, or death.

For subjects in Part A and Part B, this analysis period starts at the first study injection on Day 1 and continues through the earliest date of study completion, discontinuation from the study, or death.

**Unscheduled visits:** Unscheduled visit measurements will be included in the analysis as follows:

- In scheduled visit windows per specified visit windowing rules.
- In the derivation of baseline/last on-treatment measurements.
- In the derivation of maximum/minimum on-treatment values and maximum/minimum change from baseline values for safety analyses.
- In individual subject data listings as appropriate.

**Visit windowing rules:** The analysis visit windows for protocol-defined visits are provided in [Appendix B](#). Results in previously vaccinated participants who received a third

Confidential

injection in the study will be presented in tables, figures, and listings at study visits related to the third injection.

**Incomplete/missing data** will be handled by the following conventions:

- Imputation rules for missing prior/concomitant medications, non-study vaccinations and procedures are provided in [Appendix C](#).

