### 9.2. Appendix B. Analysis Visit Windows for Safety and Immunogenicity Analysis

Safety and immunogenicity analysis will be summarized using the following analysis visit window for post-injection assessments:

Step 1: If the safety and immunogenicity assessments are collected at scheduled visit, i.e. nominal scheduled visit, the data collected at scheduled visit will be used.

Step 2: If the safety and immunogenicity assessments are not collected at the scheduled visit, assessments collected at unscheduled visit will be used using the analysis visit windows described in [Table 3](#) below.

If a subject has multiple assessments within the same analysis visit, the following rule will be used:

- If multiple assessments occur within a given analysis visit, the assessment closest to the target study day will be used.
- If there are 2 or more assessments equal distance to the target study day, the last assessment will be used.

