**Table 3. Visit Windows**

	Visit Day (Month) 	Study Injection 	Visit Window by Regimen without Booster (Part A)		
			2-Dose Unvaccinated	3-Dose Unvaccinated	3-Dose Previously Vaccinated with Moderna COVID- 19 Vaccine 
NP Swab for SARS-CoV-2 Safety Lab	1	First	≤1, Pre-dose	≤1, Pre-dose	
	29 (1)	Second	[2, 43]	[2, 43]	
	57 (2)		≥44	[44, 71]	
	85 (3)	Third		[72, 99]	≤1, Pre-dose
	113 (4)			≥100	≥2
	1	First	≤1, Pre-dose	≤1, Pre-dose	
	8		[2, 18]	[2, 18]	
	29 (1)	Second	[19, 32]	[19, 32]	
	36		[33, 46]	[33, 46]	
	57 (2)		≥47	[47, 71]	
	85 (3)	Third		[72, 88]	≤1, Pre-dose
	92			[89, 101]	[2, 18]
	113 (4)			≥102	≥19
Vital Signs	1	First	≤1, Pre-dose	≤1, Pre-dose	
	1	First	1, Post-dose	1, Post-dose	
	29 (1)	Second	[2, 29 Pre-dose]	[2, 29 Pre-dose]	
	29 (1)	Second	[29 Post-dose, 43]	[29 Post-dose, 43]	
	57 (2)		[44, 133]	[44, 71]	
	85 (3)	Third		[72, 85 Pre-dose]	≤1, Pre-dose
	85 (3)	Third		[85 Post-dose, 99]	1, Post-dose
	113 (4)			[100, 189]	[2, 104]
	180 (6)				
	209 (7)		[134, 301]		
	265 (9)			[190, 357]	[105, 272]
	365 (12)				
	394 (13)		≥302		

	450 (15)			$\geq 358$	$\geq 273$
Immunogenicity	1	First	$\leq 1$ , Pre-dose	$\leq 1$ Pre-dose	
	29 (1)	Second	[2, 43]	[2, 43]	
	57 (2)		[44, 133]	[44, 71]	
	85 (3)	Third		[72, 99]	$\leq 1$ , Pre-dose
	113 (4)			[100, 189]	[2, 104]
	180 (6)				
	209 (7)		[134, 301]		
	265 (9)			[190, 357]	[105, 272]
	365 (12)				
	394 (13)		$\geq 302$		
	450 (15)			$\geq 358$	$\geq 273$

1. Visit day is the target day.
2. Second study injection only applicable to 2-dose unvaccinated and 3-dose unvaccinated participants.
3. Third study injection only applicable to 3-dose unvaccinated participants. SOT recipients who were previously vaccinated with 2 doses of Moderna COVID-19 vaccine prior to enrollment will receive dose 3 (first study injection) on Day 1.

	Visit Day (Month/Study Visit Day During BD Phase) 	Study Injection 	Visit Window by Regimen with Booster (Part A + Part B)			
			2-Dose Unvaccinated with Booster	3-Dose Unvaccinated with Booster	3-Dose Previously Vaccinated with Moderna COVID-19 Vaccine with Booster 	Previously Vaccinated with COVID-19 Vaccine outside of the study with Booster 
NP Swab for SARS-CoV-2	1	First	≤1, Pre-dose	≤1, Pre-dose		
	29 (1)	Second	[2, 43]	[2, 43]		
	57 (2)		[44, End of Part A]	[44, 71]		
	85 (3)	Third		[72, 99]	≤1, Pre-dose	
	113 (4)			[100, End of Part A]	[2, End of Part A]	

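### SAP Table 3 lets an unscheduled post-dose sample fill a missing pre-dose Day 29 or Day 85 antibody value, and lets 28-day values come from well outside the visit windows

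*SAP*

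**What the plan says.** SAP Appendix B assigns samples to visits in two steps. The scheduled sample comes first: "If the safety and immunogenicity assessments are collected at scheduled visit, i.e. nominal scheduled visit, the data collected at scheduled visit will be used". If there is none, "assessments collected at unscheduled visit will be used using the analysis visit windows described in" Table 3. SAP Section 6.1 agrees, placing unscheduled measurements "In scheduled visit windows per specified visit windowing rules". With several candidates, the one nearest the target day is taken; at equal distance, the last.

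For immunogenicity, Table 3 gives:

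- Day 29: Days 2 to 43. Day 85: Days 72 to 99. Neither row separates pre-dose from post-dose.
- 28 days after the last Part A dose: Days 44 to 133 (2-dose, Day 57), Days 100 to 189 (3-dose, Day 113), Days 2 to 104 (previously vaccinated Group A3, Day 29). In boosted participants each of these runs to the end of Part A.
- BD-Day 29: BD-Days 2 to 105.
- Day 1 and BD-Day 1: pre-dose or pre-booster only.

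The vital-signs rows of the same table are split at the injection, for example "29 Post-dose, 43".

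In the protocol's 3-dose schedule (Section 10.1, Table 8), immunogenicity samples "must be collected prior to dosing on Day 1, Day 29, and Day 85"; the 2-dose schedule has the same rule for Day 1 and Day 29. Section 3.1 gives the first two doses "28 days apart (window of -3/+7 days for the second dose") and the third "at Day 85 (window of -3/+7 days for the third dose").

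**The concern.** On dosing days the protocol wants the antibody level just before the next injection. The substitution rule would accept a sample drawn after that injection and report it as the Day 29 or Day 85 value. The tie rule can prefer it: of two unscheduled samples on Days 19 and 39, both 10 days from target, the Day 39 sample is used, 10 days after a Day 29 dose.

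The geometric means, fold rises and fold-rise proportions at Days 29 and 85 are secondary summaries. A post-dose value would blur what they describe, above all the level before dose 3. At the 28-day points, a substitute could come from days or months after the dose and still be summarised as a 28-day response.

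**Working it through.** **Where the bounds come from.** Each upper bound in Table 3 is the midpoint of two consecutive target days, rounded down:

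- (29 + 57)/2 = 43
- (57 + 85)/2 = 71
- (85 + 113)/2 = 99
- (57 + 209)/2 = 133
- (113 + 265)/2 = 189
- (29 + 180)/2 = 104.5, so 104
- (29 + 181)/2 = 105 (booster)

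All match. Dosing days do not enter the construction.

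**Post-dose days inside the pre-dose windows.** The Part A days are read as counted from the first injection.

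- Day 29 window: 43 - 2 + 1 = 42 days. Dose 2 on Day 29 leaves 43 - 29 = 14 days after the dose (14/42 = 33%). Dosing on Day 26 leaves 17; on Day 36, 7.
- Day 85 window: 99 - 72 + 1 = 28 days. Dose 3 on Day 85 leaves 99 - 85 = 14 days after the dose (14/28 = 50%). Dosing on Day 82 leaves 17; on Day 92, 7.

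**Late doses.** Protocol Section 10.1 allows a pandemic extension to Day 29 or Day 85 plus 21 days, that is, Day 50 or Day 106. The label then fails the other way: Days 44 to 49, or 100 to 105, precede the dose but fall in the Day 57 or Day 113 window. A cut at a fixed day would not cure this.

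**Width of the 28-day windows.** Days since dose = bound minus nominal dose day. Visit windows are from protocol Tables 7 to 10.

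| Time point | SAP window | Days since dose | Protocol visit window | SAP days outside it |
|---|---|---|---|---|
| 2-dose Day 57 | 44 to 133 (90 days) | 15 to 104 | +7: Days 57 to 64 (8 days) | 82/90 = 91% |
| 3-dose Day 113 | 100 to 189 (90 days) | 15 to 104 | -3/+7: Days 110 to 120 (11 days) | 79/90 = 88% |
| A3 Day 29 | 2 to 104 (103 days) | 1 to 103 | ±3: Days 26 to 32 (7 days) | 96/103 = 93% |
| BD-Day 29 | 2 to 105 (104 days) | 1 to 104 | -3/+14: Days 26 to 43 (18 days) | 86/104 = 83% |

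These are shares of calendar days in a window, not of samples.

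**Which off-schedule blood exists.** Protocol Section 7.1.6 says of the illness visit: "During this visit, a blood sample will also be collected for immunologic assessment of SARS-CoV-2". The footnotes to the schedules of events narrow this to binding antibody against nucleocapsid. A convalescent sample is drawn 28 to 35 days after diagnosis for a possible immunologic assessment, with no assay named. By timing alone, such a visit falls in the BD-Day 29 window for a diagnosis up to BD-Day 77 (105 - 28), or BD-Day 70 if it takes place at 35 days (105 - 35).

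**The case against.** The best defence is that the error needs an unlikely chain. The pre-dose sample must be missed at the dosing visit, the dose given anyway, and an unscheduled sample tested for spike or neutralizing antibody within about two weeks. The extra blood planned in those intervals (Days 36 and 92) is for safety laboratory tests and cell-mediated immunity, and it is drawn at scheduled visits. This stands: it makes the event rare, though the written rule still allows it.

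The vital-signs comparison is also weaker than it looks. Those rows are split because vital signs are planned both before and after injection, and the nasopharyngeal swab rows use the same unsplit windows. The comparison shows that the table can carry a split, not that one was forgotten.

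A reader might infer that post-infection samples can displace the primary result. The documents do not support that. The primary endpoint is neutralizing antibody, measured by its own pseudovirus assay (SAP Appendix G). The multiplex panel that covers spike and nucleocapsid together could yield a spike value from an illness sample, but nothing says that illness samples go through it; the infection endpoints use the Roche Elecsys assay. Nor do the windows create the infection issue: the mITT and PP Immunogenicity Sets screen for infection only at baseline or pre-booster, so an on-time scheduled sample after a breakthrough infection is kept just the same.

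Finally, the PP Immunogenicity Set requires compliance with sampling times (SAP Sections 5.2.3 and 5.3.3). That is a partial guard. It states no day limits, and the major-deviation rules are still to be finalised (Section 6.2.7). The mITT sensitivity analysis (Section 6.4) has no timing condition.

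**Conclusion.** The point holds as a statement of what the SAP permits. A substitute for a missing Day 29 or Day 85 sample can be taken up to 14 days after a dose given on the nominal day, or 7 to 17 days across the ordinary dosing window. A substitute for a 28-day value can come from 1 to about 104 days after the dose in Group A3 and the booster phase, and from about 15 to 104 days at 2-dose Day 57 and 3-dose Day 113. It would be wrong to apply the 1-to-104-day span to all four.

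It would also be wrong to infer that baselines are contaminated. Day 1 and BD-Day 1 are restricted to pre-dose values, so the reference levels for fold rise are safe from this rule.

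The practical effect is confined to missing scheduled samples, and the documents give no basis for counting them. The neutralizing antibody results are reached only if that assay is run on an off-schedule sample. In a descriptive study without hypothesis tests this is a minor correction, worth making because it costs almost nothing before database lock.

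**What to change.** In SAP Table 3 and Appendix B:

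1. End the Day 29 and Day 85 immunogenicity windows at the actual date and time of dose 2 and dose 3. List, but do not summarise, unscheduled samples taken after that dose and before the next window opens.
2. For the 28-day time points, accept a substitute only within the protocol visit window for that visit (for example -3/+14 days for BD-D29). Where the dose was delayed, count from the actual dose date, as protocol Section 7.1.1 does for clinic visits. This also replaces the open end of the Part A windows in boosted participants.
3. State that illness and convalescent samples are not used as substitutes for scheduled immunogenicity samples.

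Apply the same rules in the PP Immunogenicity and mITT analyses. The cost is a table edit and a sentence or two. The downside is a few more missing values.

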**Table 3. Visit Windows**

	Visit Day (Month) 	Study Injection 	Visit Window by Regimen without Booster (Part A)		
			2-Dose Unvaccinated	3-Dose Unvaccinated	3-Dose Previously Vaccinated with Moderna COVID- 19 Vaccine 
NP Swab for SARS-CoV-2 Safety Lab	1	First	≤1, Pre-dose	≤1, Pre-dose	
	29 (1)	Second	[2, 43]	[2, 43]	
	57 (2)		≥44	[44, 71]	
	85 (3)	Third		[72, 99]	≤1, Pre-dose
	113 (4)			≥100	≥2
	1	First	≤1, Pre-dose	≤1, Pre-dose	
	8		[2, 18]	[2, 18]	
	29 (1)	Second	[19, 32]	[19, 32]	
	36		[33, 46]	[33, 46]	
	57 (2)		≥47	[47, 71]	
	85 (3)	Third		[72, 88]	≤1, Pre-dose
	92			[89, 101]	[2, 18]
	113 (4)			≥102	≥19
Vital Signs	1	First	≤1, Pre-dose	≤1, Pre-dose	
	1	First	1, Post-dose	1, Post-dose	
	29 (1)	Second	[2, 29 Pre-dose]	[2, 29 Pre-dose]	
	29 (1)	Second	[29 Post-dose, 43]	[29 Post-dose, 43]	
	57 (2)		[44, 133]	[44, 71]	
	85 (3)	Third		[72, 85 Pre-dose]	≤1, Pre-dose
	85 (3)	Third		[85 Post-dose, 99]	1, Post-dose
	113 (4)			[100, 189]	[2, 104]
	180 (6)				
	209 (7)		[134, 301]		
	265 (9)			[190, 357]	[105, 272]
	365 (12)				
	394 (13)		≥302		

	450 (15)			$\geq 358$	$\geq 273$
Immunogenicity	1	First	$\leq 1$ , Pre-dose	$\leq 1$ Pre-dose	
	29 (1)	Second	[2, 43]	[2, 43]	
	57 (2)		[44, 133]	[44, 71]	
	85 (3)	Third		[72, 99]	$\leq 1$ , Pre-dose
	113 (4)			[100, 189]	[2, 104]
	180 (6)				
	209 (7)		[134, 301]		
	265 (9)			[190, 357]	[105, 272]
	365 (12)				
	394 (13)		$\geq 302$		
	450 (15)			$\geq 358$	$\geq 273$

1. Visit day is the target day.
2. Second study injection only applicable to 2-dose unvaccinated and 3-dose unvaccinated participants.
3. Third study injection only applicable to 3-dose unvaccinated participants. SOT recipients who were previously vaccinated with 2 doses of Moderna COVID-19 vaccine prior to enrollment will receive dose 3 (first study injection) on Day 1.

	Visit Day (Month/Study Visit Day During BD Phase) 	Study Injection 	Visit Window by Regimen with Booster (Part A + Part B)			
			2-Dose Unvaccinated with Booster	3-Dose Unvaccinated with Booster	3-Dose Previously Vaccinated with Moderna COVID-19 Vaccine with Booster 	Previously Vaccinated with COVID-19 Vaccine outside of the study with Booster 
NP Swab for SARS-CoV-2	1	First	≤1, Pre-dose	≤1, Pre-dose		
	29 (1)	Second	[2, 43]	[2, 43]		
	57 (2)		[44, End of Part A]	[44, 71]		
	85 (3)	Third		[72, 99]	≤1, Pre-dose	
	113 (4)			[100, End of Part A]	[2, End of Part A]	
	Booster Phase (Part B)					
	BD-Day 1	BD	≤1, Pre-booster	≤1, Pre-booster	≤1, Pre-booster	≤1, Pre-booster
	1	First	≤1, Pre-dose	≤1, Pre-dose		
Safety Lab	8		[2, 18]	[2, 18]		
	29 (1)	Second	[19, 32]	[19, 32]		
	36		[33, 46]	[33, 46]		
	57 (2)		[47, End of Part A]	[47, 71]		
	85 (3)	Third		[72, 88]	≤1, Pre-dose	
	92			[89, 101]	[2, 18]	
	113 (4)			[102, End of Part A]	[19, End of Part A]	
	Booster Phase (Part B)					
Vital Signs	BD-Day 1	BD	≤1, Pre-booster	≤1, Pre-booster	≤1, Pre-booster	≤1, Pre-booster
	BD-Day 8		[2, 18]	[2, 18]	[2, 18]	[2, 18]
	BD-Day 29		≥19	≥19	≥19	≥19
	1	First	≤1, Pre-dose	≤1, Pre-dose		
	1	First	1, Post-dose	1, Post-dose		
	29 (1)	Second	[2, 29 Pre-dose]	[2, 29 Pre-dose]		
	29 (1)	Second	[29 Post-dose, 43]	[29 Post-dose, 43]		
	57 (2)		[44, End of Part A]	[44, 71]		
Booster Phase (Part B)						

Immunogenicity	BD-Day 1	BD	$\leq 1$ , Pre-booster			
	BD-Day 1	BD	1, Post-booster	1, Post-booster	1, Post-booster	1, Post-booster
	BD-Day 8		[2, 18]	[2, 18]	[2, 18]	[2, 18]
	BD-Day 29		[19, 105]	[19, 105]	[19, 105]	[19, 105]
	BD-Day 181		$\geq 106$	$\geq 106$	$\geq 106$	$\geq 106$
	1	First	$\leq 1$ , Pre-dose	$\leq 1$ , Pre-dose		
	29 (1)	Second	[2, 43]	[2, 43]		
	57 (2)		[44, End of Part A]	[44, 71]		
	85 (3)	Third		[72, 99]	$\leq 1$ , Pre-dose	
	113 (4)			[100, End of Part A]	[2, End of Part A]	
Booster Phase (Part B)						
	BD-Day 1	BD	$\leq 1$ , Pre-booster			
	BD-Day 29		[2, 105]	[2, 105]	[2, 105]	[2, 105]
	BD-Day 181		$\geq 106$	$\geq 106$	$\geq 106$	$\geq 106$

1. Visit day is the target day.
2. Second study injection only applicable to 2-dose unvaccinated with booster and 3-dose unvaccinated participants with booster. Third study injection only applicable to 3-dose unvaccinated participants with booster.
3. SOT recipients who were previously vaccinated with 2 doses of Moderna COVID-19 vaccine will receive dose 3 (first study injection) on Day 1.
4. SOT recipients who were previously vaccinated with mRNA or non-mRNA COVID-19 vaccine primary series (outside of the study) will receive BD (first study injection) on BD-Day 1.
5. Visit window for booster phase (Part B) will be based on booster dose (assessment date – date of BD +1).

